3.4 Dose Modifications

All toxicity grades below are described using the NCI Common Terminology Criteria for Adverse Events (CTCAE) version 4.0.

All appropriate treatment areas should have access to a copy of the CTCAE version 4.0. A copy of the CTCAE version 4.0 can be downloaded from the CTEP website (http://ctep.cancer.gov).

Dose interruption and/or dose modification in 12.5 mg increments or decrements is recommended based on individual safety and tolerability.

The acceptable dose levels for sunitinib therapy are listed below in the following table. Treatment is initiated at dose level 0, if a dose reduction occurs for grade II or III toxicity, and a patient tolerates the dose reduction well, and is deriving clinical benefit, a dose level escalation back to the prior dose may be considered after 1 cycle.

Dose Level	Dose and Administration Schedule
0	50mg po daily for 4 weeks, 2 weeks rest
-1	37.5 mg po daily for 4 weeks, 2 weeks rest
-2	25 mg po daily for 4 weeks, 2 weeks rest
-3	Discontinue therapy

If the drug is held longer than 2 weeks (excluding 2 week rest period), discontinue sunitinib.

Specific dose modification criteria and management in response to specific toxicities are listed in the table below:

Table 1. Sunitinib Dose-Reduction Guidelines

Toxicity	Sunitinib Modification
Skin and Subcutaneous Disorders	
Palmar-plantar erythrodysesthesia syndrome (PPE) (hand-foot syndrome)	See table 2 below 'Sunitinib Dose Reductions for PPE (Hand-Foot Syndrome)'
Grade 3 or 4 rash acneiform	 Hold sunitinib Re-evaluate at least weekly until resolution to ≤ grade 1 or tolerable grade 2 Re-start sunitinib at one dose-reduction step If AE persists > 14 days, discontinue sunitinib If grade 4 acneiform rash (related to sunitinib), sunitinib may be discontinued at investigator's discretion
Stevens-Johnson syndrome or toxic epidermal necrolysis	Discontinue sunitinib if Stevens-Johnson syndrome or toxic epidermal necrolysis are suspected
Gastrointestinal Disorders	
Perforation (esophageal, gastric, colonic, duodenal, ileal, jejunal, rectal, or small intestine)	Discontinue sunitinib
Investigations	
Grade 3 or 4 AST or ALT increase	 Hold sunitinib If no alternative explanation for transaminitis can be determined (such as viral hepatitis, progressive underlying hepatic malignancy), discontinue sunitinib Otherwise, upon resolution to ≤ grade 1 or baseline, re-start sunitinib at one dose-reduction step If patient develops ≥ grade 3 hepatic failure, discontinue sunitinib.
Grade 3 or 4 electrocardiogram QT corrected interval prolonged	 See also Section 3.5.4. Hold sunitinib Check and immediately administer potassium to achieve levels of ≥ 4 mmol/L and magnesium to levels of ≥ 2 mg/dL Consider chronic oral supplementation of potassium and/or magnesium Review with the subprotocol principal investigator and consult with a cardiologist prior to patient's next scheduled treatment, considering the following options: HOLD sunitinib until QTc recovers to pre-study treatment baseline (grade 1 or less, or ≤ 480ms) When QTc returns to baseline, reinitiate sunitinib cautiously, with additional QTc monitoring at earliest possible follow-up opportunity, but no more than 8 days from reintroduction of sunitinib If QTc prolongation event felt attributable to sunitinib, follow protocol dose-reduction-step guidelines (see table above in Section 3.4) when re-introduced For recurrent QTc grade 3 felt attributable to sunitinib despite dose-step reduction, discontinue sunitinib

EAY131-V
Version Date: November 10, 2022
NCI Update Date: August 12, 2015

	Monitor urine protein once every cycle with urinalysis. If protein excretion positive on urinalysis, obtain 24-hour urine protein.
Proteinuria	Interrupt treatment for 24-hour urine protein ≥ 3 grams. Discontinue for repeat episodes of protein ≥ 3 grams despite dose reductions or nephrotic syndrome.
Nervous System Disorders (poter	
Grade 2 pre-syncope or grade 3 syncope	 See also Section 3.5.2. Obtain ECG for cardiology review/consultation Check magnesium and potassium and promptly administer potassium to achieve level of ≥ 4 mmol/L and magnesium to level ≥ 2 mg/dL IF ECG shows new dysrhythmia or QTc ≥ grade 2 (> 480ms), hospitalize for monitoring with cardiology consultation HOLD sunitinib until any potassium and magnesium abnormalities are corrected, symptoms resolved and QTc returns to grade 1 or less (≤ 480ms) Reintroduce sunitinib cautiously, with input from cardiology and with additional QTc evaluation, either concurrent with reintroduction or at earliest possible follow-up opportunity and no more than 8 days from reintroduction If event felt attributable to sunitinib consider dose modification of sunitinib when re-introduced Consider chronic oral supplementation of potassium and/or magnesium For recurrent syncope or near-syncope felt attributable to sunitinib consider permanent discontinuation
All Other Non-Hematologic Toxici	ties Attributable to sunitinib
Any grade 2 non-hematologic toxicity that is persistent, intolerable, or unresponsive to optimal management	At the treating investigator's discretion, reduce to the next lower dose-reduction step
Grade 3 or 4	 Omit sunitinib until resolution to ≤ grade 1, baseline or tolerable grade 2 Re-start sunitinib at one dose-reduction step If AE persists > 14 days, discontinue sunitinib In addition, at investigator discretion: For bleeding that requires more than minor medical intervention, consider discontinuing sunitinib For severe persistent hypertension or hypertensive crisis despite optimal antihypertensive management, consider discontinuing sunitinib For evidence of cardiac ischemia or myocardial infarction, consider discontinuing sunitinib For grade 4 AEs related to sunitinib, consider discontinuing sunitinib

NCI Update Date: August 12, 2015

Dose reduction guideline table for Plantar Palmar Erythrodysesthesia

Table 2. Sunitinib Dose-Reduction Guidelines and Management for PPE

Grade	Occurrence	Action
Grade 1	1 st occurrence or recurrence	Continue sunitinib and institute supportive measures for symptomatic relief.*
Grade 2: Moderate and painful skin changes of hands and/or feet such as peeling, blisters, bleeding,	1 st or 2 nd occurrence	Continue sunitinib and institute supportive measures for symptomatic relief.* If no improvement within 7 days, see below.
hyperkeratosis, erythema, swelling; and/or any such changes that are limiting instrumental activities of daily living (preparing meals, shopping for groceries, using the telephone, managing money, etc)	No improvement within 7 days or recurrence beyond 2 nd occurrence	Stop sunitinib treatment until toxicity resolves to grade 0-1. When resuming treatment, decrease sunitinib dose by 1 dose-reduction step.
	Coourtenee	Institute supportive measures for symptomatic relief.*
Grade 3: Severe and painful skin changes of the hands and/or feet, such as moist desquamation, ulceration, blistering, bleeding, hyperkeratosis, erythema, swelling;	1 st or 2 nd occurrence	Stop sunitinib treatment until toxicity resolves to grade 0-1. When resuming treatment, decrease s sunitinib by 1 dose-reduction step.
and/or any such severe changes or pain that are limiting self-care		Institute supportive measures for symptomatic relief.*
activities of daily living (bathing, dressing, feeding self, using toilet, taking medications or becoming bedridden)	3 rd occurrence	Discontinue sunitinib treatment.

^{*}See section 3.5.3 for PPE management

Table 3. Other Hematologic and Non-Hematologic Adverse Events

Event	AE Grade or Observation	Dose modification
	Grades 1 and 2	Maintain dose
Neutropenia	Grade 3*	Hold sunitinib until ≤ grade 2, then resume at same dose level
	Grade 4	Hold sunitinib until ≤ grade 2, then reduce 1 dose level and resume treatment
	Grades 1 and 2	Maintain dose
Thrombocytopenia	Grade 3* and severe grade 2, at investigator discretion	Hold sunitinib until ≤ grade 2, then reduce 1 dose level and resume treatment
	Grade 4	Hold sunitinib until ≤ grade 2, then reduce 1 dose level and resume treatment

^{*}Recurrent grade 3 events require dose reduction.

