 - Grade 1 (450-480 ms), follow-up QTc evaluation should be done within 8 days after concurrent use starts.
 - Grade 2 (481-500 ms), withhold study drug until followup ECG at next possible opportunity shows QTc ≤ grade 1 (≤ 480 ms); evaluate QTc within 8 days after reintroduction of study drug.

- 3.5.4.4 Any new onset of dysrhythmia on ECG during therapy will be reviewed and managed with input from cardiology.
- 3.5.4.5 For any episode of syncope (grade 3) or near-syncope (pre-syncope grade 2) or QTc grade 3 or 4 (> 500 ms on 2 ECGs), see Table 1 in section 3.4

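### The stopping line for recurrent QTc prolongation names grade 3 but not grade 4, so read literally it is stricter on the milder recurrence

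*Protocol*

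**What the plan says.** The Table 1 row in Protocol section 3.4 is headed "Grade 3 or 4 electrocardiogram QT corrected interval prolonged", and section 3.5.4.5 sends both grades to it: "QTc grade 3 or 4 (> 500 ms on 2 ECGs), see Table 1 in section 3.4".

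For either grade the row says to hold sunitinib and correct potassium and magnesium. It then asks for a consultation: "Review with the subprotocol principal investigator and consult with a cardiologist prior to" the patient's "next scheduled treatment, considering the following options". Treatment may restart once QTc has recovered. For the restart dose the row says: "If QTc prolongation event felt attributable to sunitinib, follow protocol dose-reduction-step guidelines".

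The only line in the row that calls for stopping is: "For recurrent QTc grade 3 felt attributable to sunitinib despite dose-step reduction, discontinue sunitinib".

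The dose levels in section 3.4 are 50 mg, 37.5 mg and 25 mg, with discontinuation at level -3. Sunitinib is also stopped after any hold of more than 2 weeks, not counting the planned rest.

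**The concern.** A row that covers two grades gives a stopping instruction for the milder one only. A site following the text would stop a patient whose grade 3 prolongation recurs on a reduced dose, but would hold and step down a patient whose recurrence is grade 4. That order is the reverse of what safety requires, and the protocol gives no reason for it.

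The toxicity is serious. The safety profile in section 1.1 describes the QT effect of sunitinib as dose-dependent and links it to ventricular arrhythmia, including Torsade de Pointes. It also reports that an NCI action letter on this risk led to amended sunitinib protocols. What is at stake is patient safety. The primary endpoint is not affected.

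**Working it through.** The protocol gives no figure to reproduce. The check compares the relevant texts, traces the rule, and then bounds the number of patients.

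**1. Could grade 3 here mean grade 3 or higher?** Section 3.4 marks that meaning when it intends it:

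- The transaminase row just above the QTc row: "If patient develops ≥ grade 3 hepatic failure, discontinue sunitinib".
- The syncope row: "IF ECG shows new dysrhythmia or QTc ≥ grade 2 (> 480ms), hospitalize for monitoring with cardiology consultation".
- The acneiform rash row also covers grades 3 and 4, and it gives grade 4 its own discontinuation line.
- The Table 3 footnote on recurrent grade 3 events leaves out grade 4 sensibly, because grade 4 has separate lines in that table. The QTc row has no such line.

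A comparison sign lost when the PDF was read is unlikely, since such signs survive elsewhere in the same row.

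**2. Does other text supply the stop?**

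- Section 3.5.4.5 only points back to the row.
- The general line on grade 4 events sits under the heading for all other non-hematologic toxicities, whereas QTc has its own row. It also asks only that discontinuation be considered.
- The 2-week hold limit depends on the length of the hold, and level -3 on the dose reached. Neither depends on a grade 4 recurrence.
- Unacceptable toxicity, in section 3.6, is left to judgment.

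**3. Rule trace.** Assumptions: the first attributable event occurs at 50 mg, there is no re-escalation, QTc recovers each time, no hold exceeds 2 weeks, and the stopping line is binding.

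| Grade of recurrence | Dose path | Events until stop | Rechallenges |
|---|---|---|---|
| 3 | 50 → 37.5 mg → stop | 2 | 1 |
| 4 | 50 → 37.5 → 25 mg → level -3 | 3 | 2 |

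Difference: 2 − 1 = 1 extra rechallenge for the worse recurrence. If the line is only one of the options for the review, both grades are decided case by case and the difference can be 0. The range is 0 to 1.

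**4. Patients affected.** Inputs: an accrual goal of 35 (Schema), QTc prolongation in the under-3% column of the CAEPR (section 3.3), and Torsade de Pointes below 0.1% (section 1.1).

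- Any QTc prolongation: fewer than 35 × 0.03 = 1.05 patients.
- Grade 4 recurrence on a reduced dose: the protocol gives no rate. With an assumed share of 5% to 25% of those patients, the expected number is below 1.05 × 0.05 = 0.05 to 1.05 × 0.25 = 0.26.
- Torsade de Pointes: fewer than 35 × 0.001 = 0.035 patients.

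**The case against.** The strongest reply is that the literal reading is not forced. No line orders a rechallenge after a recurrent grade 4 event. The subprotocol PI and a cardiologist must review the case before the next treatment, and the stopping line may be one of the options put to them; the extracted text no longer shows the bullet levels. Section 3.4 also describes dose modification as a recommendation. A clinician would probably treat a recurrent grade 4 event as at least meeting the grade 3 criterion. This stands, and it is why the lower end of the range is 0. Even as an option, however, discontinuation is named only for the milder recurrence.

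Re-escalation is a second point. Section 3.4 allows a return to the previous dose after a reduction for grade II or III toxicity, but does not offer it after grade IV. A patient first reduced for grade 3 could go back to 50 mg, and a new event there might not count as occurring despite a reduction. The gap of one rechallenge could then shrink or reverse. The trace is valid only without re-escalation.

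Other safeguards also remain: the general stops, cardiology input for any new dysrhythmia (section 3.5.4.4), and hospitalization under the syncope row when the ECG shows new dysrhythmia or QTc of grade 2 or worse. In addition, the under-3% figure comes from sunitinib patients in general, while this trial excludes clinically important resting ECG abnormalities and arrhythmia within 12 months. All of this lowers the practical risk, but none of it supplies the missing grade 4 instruction.

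**Conclusion.** The concern holds. The row covers grades 3 and 4, its only stopping line names grade 3, and nothing elsewhere sets a stop for recurrent grade 4. Followed as written, the rule can be more lenient on the worse event.

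The practical effect is small: 0 to 1 extra rechallenge per affected patient, under the conditions of the trace, and an expected number of such patients well below one. That last figure rests on an assumed recurrence share. The wording should still be corrected, because it is a safety rule for a potentially fatal, dose-dependent toxicity and the likely intent differs from the text. Confidence is medium, mainly because it is unclear whether the line is binding or optional.

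**What to change.** In the QTc row of Table 1, extend the last line so that a recurrence of grade 3 or 4, judged attributable to sunitinib and occurring despite a dose step, leads to discontinuation. Nothing else in the row has to change.

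The cost is two added words (or 4) in an addendum, with no extra patients, visits, ECGs or data. The one drawback is that a very few patients may stop treatment earlier than under the present wording.

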3.5.3.2 PPE Treatment

- Treatment may begin at the first clinical signs of PPE. At first occurrence, independent of grade, supportive measures should be promptly initiated. Tender areas should be protected as follows:
- Use socks/gloves to cover moisturizing creams
- Wear well-padded footwear; use insole cushions or inserts.
- Foot soaks with tepid water and Epson salts.
- Creams may be used as follows:
- Non-urea based creams may be applied liberally.
- Keratolytic creams (eg, urea-based creams, salicylic acid 6%) may be used sparingly and only to affected hyperkeratotic areas.

- Alpha hydroxyl acids (AHA)-based creams may be applied liberally 2 times a day. Approximately 5% to 8% provides gentle chemical exfoliation.
- Topical analgesics (eg, lidocaine 2%) may be used for pain control.
- Topical corticosteroids like clobetasol 0.05% should be considered for patients with grade 2 or 3 PPE.
 Systemic steroids should be avoided.
- Use of celecoxib: A meta-analysis of PPE prevention strategies concluded that celecoxib, with statistically significant results, was the most promising agent. Therefore, celecoxib can be considered to reduce the severity of PPE as follows: Celecoxib 200 mg once daily should begin at the first clinical signs or symptoms of grade 2 or greater PPE.
- 3.5.4 QT Prolongation Considerations During Therapy
 - 3.5.4.1 Any time QTc is evaluated:
 - When HR is between 60-100 bpm, no manual read of QTc required
 - When HR < 60 or >100 bpm, manual read of QTc by member of the study team is required, using Fridericia correction
 - 3.5.4.2 To the extent possible, concurrent use of sunitinib with drugs known to cause clinically significant QT prolongation should be avoided. Such drugs may be identified with reference to Appendix III in the subprotocol, in addition to the Credible Meds website (http://crediblemeds.org/login). The Credible Meds website requires free user registration to view the list of clinically relevant QT prolonging drugs, eg, those known to carry a risk of causing Torsade de Pointes. QT prolonging drugs to be avoided during this trial are shown in the Credible Meds list of "drugs with known TdP risk."
 - 3.5.4.3 When concurrent use of sunitinib with any drug on the Credible Meds list of "drugs with known TdP risk" cannot be avoided, review QTc prior to concurrent use. If preconcurrent use QTc is:
 - Grade 0 (< 450 ms), follow-up QTc evaluation should be done at the next scheduled follow-up visit.

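### Table 1's syncope row lets a restart-day QTc count as the only recheck, so after an event QTc of 481-500 ms the subprotocol may require no later reading on resumed sunitinib (low priority)

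*Protocol*

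**What the plan says.** The pre-syncope/syncope row of Table 1 (Protocol Section 3.4) begins at the event: "Obtain ECG for cardiology review/consultation". It also calls for correction of potassium and magnesium, and for hospital monitoring if there is a new dysrhythmia or QTc exceeds 480 ms. Sunitinib is held until electrolytes are corrected, symptoms have resolved and QTc is 480 ms or less. Restart is to be cautious, with cardiology input and an additional QTc evaluation "either concurrent with reintroduction or at earliest possible follow-up opportunity and no more than 8 days from reintroduction". A dose change is optional: "If event felt attributable to sunitinib consider dose modification of sunitinib when re-introduced".

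Two other rules deal with QTc at restart.

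- The grade 3/4 QTc row of the same table calls for restart "with additional QTc monitoring at earliest possible follow-up opportunity, but no more than 8 days from reintroduction of sunitinib". Section 3.5.4.5 describes that trigger as "QTc grade 3 or 4 (> 500 ms on 2 ECGs), see Table 1".
- Section 3.5.4.3, for grade 2 (481-500 ms), says "evaluate QTc within 8 days after reintroduction of study drug". That section begins "When concurrent use of sunitinib with any drug on the Credible Meds list of" drugs with known torsade risk, and it applies only when such use cannot be avoided.

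The longest hold is also fixed in Section 3.4: "If the drug is held longer than 2 weeks (excluding 2 week rest period), discontinue sunitinib".

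**The concern.** Both of the other rules place the recheck after dosing has resumed. The syncope row alone accepts a reading taken at the moment of restart. The hold ends only once QTc is 480 ms or less, so a restart-day ECG largely repeats the reading that ended the hold. It says little about QTc under resumed dosing.

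Section 1.1 states that sunitinib prolongs QT in a dose-dependent manner. The patient at issue has just had syncope or near-syncope with a QTc that the row itself treats as needing hospital monitoring, and may go back to the same daily dose. Prolongation that returned without symptoms could go unnoticed although every step of the row had been followed.

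**Working it through.** The plan gives no figure to reproduce here, so the check has three parts: which rules apply, how much drug is present at each possible reading, and how many patients are concerned.

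**1. Which rule requires a later QTc when the event QTc is 481-500 ms?**

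| Rule | Does it reach this patient? |
|---|---|
| Syncope row, Table 1 | Yes, but a restart-day ECG satisfies it |
| Grade 3/4 QTc row, Table 1 | No: the trigger is above 500 ms on 2 ECGs |
| Section 3.5.4.3, grade 2 | Only with a concurrent drug of known torsade risk |
| Section 3.5.4.5 | Sends syncope back to Table 1 |
| Section 3.5.2, to which the syncope row cross-refers | No: it deals with hypertension |

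The ECG mark in the Section 4.1 schedule is garbled and nothing here rests on it. If it means an ECG before each cycle, that ECG follows the 14-day rest, when 2^(-336/41) = 0.3% to 2^(-336/86) = 6.7% of drug is left. It would not be an on-drug reading.

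**2. Drug present at the reading.** The inputs are the half-life t = 41 to 86 h (Section 1.1), once-daily dosing, and a hold of H days, up to 14 (Section 3.4). The model has one compartment and covers the parent drug only. Results are given as 41 h / 86 h.

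Resumed drug as a share of its own steady state is 1 - 2^(-h/t):

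- before the first resumed dose: 0% / 0%
- 24 h (first dosing interval): 33.4% / 17.6%
- 192 h (day 8): 96.1% / 78.7%

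Total drug as a share of the pre-hold level assumes steady state before the hold and the same dose after it. At restart it is r = 2^(-24H/t). After h hours it is 1 - (1 - r) × 2^(-h/t).

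| Hold | At restart | Day 8 |
|---|---|---|
| 1 day | 66.6% / 82.4% | 98.7% / 96.3% |
| 2 days | 44.4% / 67.9% | 97.8% / 93.2% |
| 7 days | 5.8% / 25.8% | 96.3% / 84.2% |
| 14 days | 0.3% / 6.7% | 96.1% / 80.1% |

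After a one-day hold the restart reading is not far from full exposure. After a week it is close to off drug. The protocol gives no typical hold length.

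**3. Reach.** The accrual goal is 35. The CAEPR in Section 3.3 appears to list QTc prolongation as rare but serious, under 3% (the table is broken in the text at hand, but the term has its own entry in that column). 35 × 0.03 = 1.05, so about one patient at most with reported QTc prolongation of any kind. The patient at issue must also have syncope or pre-syncope, a QTc between 481 and 500 ms, no drug of known torsade risk, a hold longer than about a day, and a site that takes only the restart-day ECG.

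**The case against.** The row is not careless. It requires an event ECG, electrolyte correction, hospital monitoring above 480 ms, a hold until QTc recovers, and cardiology input at restart. Leaving ECG timing to the cardiologist after an event of any cause is defensible, and the CAEPR lists syncope among events with insufficient evidence that sunitinib causes them. The comparator is also softer than it first looks: in the grade 3/4 row the recheck appears among options to be considered, and an ECG at 24 h would satisfy it. A restart-day ECG taken after the dose sees some resumed drug, and after a 2-day hold 44% / 68% of the pre-hold level is still present. These points stand. They limit the weight of the concern, but they do not change the fact that the row can be met without any later reading.

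A reader might infer more than the documents support:

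- *That the rows contradict each other.* They have different triggers, so this is a weaker rule, not a conflict.
- *That no on-drug QTc is required after any syncope.* An event QTc above 500 ms falls under the grade 3/4 row, and concurrent use of a known-torsade-risk drug falls under Section 3.5.4.3. The Master Protocol, whose parameters also apply, is not shown.
- *That events early in a cycle form a second gap of equal weight.* Outside the 481-500 ms group, these are patients whose event ECG was 480 ms or less and so did not implicate QTc. By day 7 of dosing the event ECG is already at 1 - 2^(-168/t) = 94% / 74% of steady state.
- *That the recheck should wait for a minimum number of resumed doses, such as five.* No rule in the protocol has such a floor. It would be stricter than the rule for QTc above 500 ms, and it would take away the earliest-opportunity check from a patient with recent syncope.

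**Conclusion.** The point holds in a narrow form. For an event QTc of 481-500 ms without a concurrent known-torsade-risk drug, the restart-day alternative allows same-dose resumption with no later on-drug QTc required by the subprotocol as shown. The protocol's two other restart rules place that reading after reintroduction and within 8 days.

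It is a low-priority safety improvement, probably affecting fewer than about one of 35 patients. That rests on the under-3% listing and on the assumption that only some such patients also have syncope or pre-syncope; the protocol gives no rate for the combination. The exposure figures are drug shares from a one-compartment, parent-only model. They are not milliseconds, since the protocol gives no concentration-QTc relation and the active metabolite is not modelled. Required cardiology input or the Master Protocol may already provide the reading. Sample size and error rates are not affected.

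**What to change.** In the pre-syncope/syncope row of Table 1, delete the alternative that lets the evaluation coincide with restart. The row would then ask for an additional QTc evaluation after reintroduction, at the first available follow-up and within 8 days of restarting. A restart-day ECG may be kept as a baseline but should not count as the recheck. Do not add a minimum number of doses.

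The cost is one phrase in one table row. For each restarted patient, at most one ECG is moved by a few days, or added if the restart ECG is kept.
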